9.5. Assessment of Efficacy

The primary effectiveness will be measured as the percentage of subjects with complete response within the treatment area. The response rates and 95% confidence intervals will be summarized. Run-in subjects will be summarized separately.

9.6. Assessment of Safety

For safety analyses, adverse events will be summarized using frequency counts and percentages. Descriptive statistics will be provided by event type, severity and relationship to study procedures and devices. Event rates along with 95% confidence intervals will be provided based on subject or event. Individual listings of adverse events, including event type, start date, duration, severity, and device-relatedness will be provided as appropriate.

9.7. Recording Data

Source data is all information, original records of clinical findings, observations, or other activities in a clinical trial necessary for the reconstruction and evaluation of the trial. Source data are contained in source documents. All data recorded on the eCRF will be supported by a source document. Examples of source data are hospital records, clinical and office charts, laboratory notes, memoranda, subjects' diaries

or evaluation checklists, pharmacy dispensing records, recorded data from automated instruments, copies or transcriptions certified after verification as being accurate and complete, microfiches, photographic negatives, microfilm or magnetic media, x-rays, subject files, and records kept at the pharmacy, at the laboratories, and at medico-technical departments involved in the clinical trial.

This study will utilize electronic Case Report Forms (eCRFs). The study CRF is the primary data collection instrument for the study. All data requested on the CRF must be recorded. All missing data must be explained.

9.8. Deviation Handling

The investigator must notify Medtronic and the reviewing IRB of any deviation from the protocol when specific to the protection of the life or physical well-being of a subject in an emergency. Such notice must be given as soon as possible, but in no event later than 5 working days after the emergency has occurred. Except in such an emergency, prior written approval by Medtronic and the site IRB/EC is required for changes in or deviations from the plan. All deviations will be reported per the site's IRB/EC deviation policy. Should any deviations from the protocol occur, these will be reviewed by Medtronic for their clinical significance. If the event is performed without written approval from all parties, the investigator may be terminated from the study. Corrective and preventive actions and principal investigator disqualification will be included in the Clinical Study Management Plan. If further escalation is needed, it may result in Corrective and Preventive Action (CAPA), suspension, or termination. When conducting clinical research, an investigator must comply with all applicable rules and regulations. The falsification of information, actions determined to fraudulent or criminal in nature, failure to comply with investigator's responsibilities, failure to appropriately fulfill all study-related responsibilities or failure to disclose relevant financial interests may lead to the investigator being disqualified. If it is determined that there is investigator fraud, or strong evidence of fraud, the course of action may include, but is not limited to: potential exclusion from analyses, site closure, notification of the responsible IRB/EC of the actions to be taken, notification of key stakeholders and/or study team of the actions to be taken, notification of appropriate regulatory authority(ies) and/or restrictions on future participation in clinical studies. Protocol deviations identified by the Monitor during a monitoring visit should be discussed with the Principal Investigator/ Study staff involved at the time of discovery. Protocol non-compliance will be documented accordingly and communicated again in writing to the site within the follow-up letter. Monitors will also escalate the deviations significant in nature to the study manager (or designee), as soon as possible.

9.9. Subject Withdrawal or Discontinuation

Any subject who wishes to withdraw from this investigation on his/her own accord and for whatever reason is entitled to do so without obligation and prejudice to further treatment. In addition, the

Principal Investigator or study endoscopist may decide for reasons of medical prudence, to withdraw a subject.

In either event, the Principal Investigator or study endoscopist will clearly document the date and reason(s) for the subject's withdrawal from this investigation on the Study Exit CRF and should indicate whether or not he considers it related to the device.

Every attempt will be made to contact subjects who are noncompliant. Subjects will be considered "Lost to Follow-up" once the following steps have been taken:

1. Two phone calls should be made to the subject. Each attempt should be clearly documented in the source documents and the response or lack thereof should be captured.
2. If there is no response to the phone calls, then an official letter should be written to the subject. A copy of the letter should be retained in the subject's source document.
3. Additionally, the site should attempt to reach out to the subject's general practitioner to determine the status of the subject.
4. After a period of four (4) weeks, after all of the above steps have been taken, the subject will be considered "Lost to Follow-up". The sponsor should be notified and the Study Exit CRF should be completed.

All patients, regardless of failure of the primary endpoint or use of escape treatment during the trial, will be followed to study termination to assess secondary endpoints. A patient that has not been withdrawn or otherwise disqualified from the study, will have completed the study when the patient has finished all follow-up visits and the study has been terminated.

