Although preliminary, results for the long-term follow-up of this study will be shortly discussed. Sustained CR during 5 years follow-up was observed in 86% (67/78 patients). Recurrence occurred in 9% (7/78 patients, MGIN 5, HGIN 1). 5 were managed with RFA, one with ESD. Progression of baseline disease occurred in another 5% (4/78 patients; HGIN (n=1), sm-ESCC (n=3)); all were treated with ESD. Two progressor lesions were normally stained after Lugol's and with repeatedly negative biopsies, and were therefore left untreated. Later both lesions were considered suspicious for cancer and escape treatment was performed, with pathology assessment for one case showed submucosal cancer buried under normal epithelial cells. Pathology assessment for the second case is pending.

However, protocol violations during follow-up occurred in the majority of patients (59%) resulting in prolonged follow-up intervals, lesions left untreated or no adequate follow-up after detection of recurrent or progressive disease. This might have interfered with the results, and those might have been better with strict follow-up protocols.

The 12 patients with residual ESCN suffered a poorer prognosis. Fifty-eight percent (7/12 patients) developed progressive disease and were treated with either ESD (n=2) or non-endoscopic treatment (n=5), suggesting that RFA failures should directly be managed with an alternative treatment like EMR or ESD.

Therefore, to further assess the safety, effectiveness, and durability of the Barrx™ Flex Radiofrequency Ablation System for the eradication of ESCN, the current study will employ methods similar to the 2 studies reported above but with a consistent primary RFA dose of 12 J/cm² with one application and no cleaning of the coagulum, and with subsequent 5-years follow-up according to strict study protocols.

7. Product Description

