Escape treatment if residual ESCN							X	X ³

Remarks:

¹ Biopsies at 6 and 9 months will be performed only if USL are detected after CR

Medtronic Confidential

² Only recurrent or progressive disease during FU will be assessed by a second expert pathologist. This includes biopsies indicating recurrent or progressive disease, and eventual EMR/ESD/surgery specimens.

³ If persistent after 4 additional RFA sessions

⁴ Study completion is defined as when all follow-up visits have been completed, all data has been entered, reviewed, monitored, and database has been locked.

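### Section 9.9 exits a subject after one failed contact procedure and provides no later re-contact, return or end-of-study vital-status check

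*Protocol*

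**What the plan says.** Protocol Section 9.9 opens the procedure with "Every attempt will be made to contact subjects who are noncompliant". Noncompliant is not defined, and no number of missed visits is required. The steps are:

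1. "Two phone calls should be made to the subject", each documented.
2. "If there is no response to the phone calls, then an official letter should be written to the subject".
3. An approach to the "general practitioner to determine the status of the subject".
4. A wait of four weeks, counted from completion of the first three steps. The subject is then classed as lost to follow-up, and "The sponsor should be notified and the Study Exit CRF should be completed".

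The same section uses the Study Exit CRF to record withdrawal by the subject or the investigator. Table 2 (Section 9.1) places that form only in the Year 2-5 column, with the remark "Study completion is defined as when all follow-up visits have been completed".

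Section 9.9 also states: "All patients, regardless of failure of the primary endpoint or use of escape treatment during the trial, will be followed to study termination". Sections 9.4.1 and 9.4.3 keep patients who receive non-endoscopic therapy in follow-up to 5 years for the secondary endpoints.

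Neither document says whether a lost subject may resume visits, whether contact is tried again at later visits, or whether vital status is sought at the end of the study.

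**The concern.** After month 12 there are four scheduled visits, at years 2, 3, 4 and 5. A subject who cannot be found around year 2 can be exited many months before the year 3 visit. A site that follows Section 9.9 as written then has no instruction to try again at years 3, 4 or 5. Some of these subjects could be found later, because people move, change telephone number or are away for a time.

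Several secondary endpoints in Section 5.2.2 depend on events after month 12: recurrence (6), progression (7), the two durability endpoints (8 and 9) and ESCC mortality (10). Mortality does not need an endoscopy and could be learned from records. The general practitioner, however, is approached only once, when the subject is being declared lost.

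The sponsor cares about follow-up quality. Section 6.2 reports that in the preceding study "protocol violations during follow-up occurred in the majority of patients (59%) resulting in prolonged follow-up intervals", and gives strict 5-year follow-up as a feature of this trial. An exit rule with no way back works against that aim.

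**Working it through.** **The plan's own figures.** The lost-to-follow-up rule carries no number. The nearest figure is the precision in Section 13.2, a half-width of 6% to 8% with 100 subjects. It reproduces: 1.96 × √(0.80 × 0.20 / 100) = 7.8 points and 1.96 × √(0.90 × 0.10 / 100) = 5.9 points. It concerns the 12-month endpoint and is not in dispute.

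**Inputs for an illustration.** Four yearly visits (Table 2). A share d of subjects unreachable at each visit, after all the contact steps, independently between visits. The documents give no value for d. The 3% dropout cited in Section 13.2 comes from a previous study and is not stated per visit. The values 3%, 5% and 10% are therefore assumptions.

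**Share without month-60 status.**
- Exit treated as permanent: 1 − (1 − d)⁴.
- Subject kept active and free to return: d.

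**Mean share of the four visits attended.**
- Exit treated as permanent: the average of (1 − d)ᵏ for k = 1 to 4.
- Kept active: 1 − d.

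| d (assumed) | No month-60 status, permanent exit | No month-60 status, return possible | Visits attended, permanent exit | Visits attended, return possible |
|---|---|---|---|---|
| 3% | 11.5% | 3% | 92.7% | 97% |
| 5% | 18.5% | 5% | 88.1% | 95% |
| 10% | 34.4% | 10% | 77.4% | 90% |

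**The opposite extreme.** If the same share d is unreachable at every visit, the month-60 loss is d under either rule and the gap is zero. The true gap lies somewhere between this and the table.

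**Precision.** Assume 80 responders at month 12 (100 × 80%) and a proportion of 86%, the sustained complete response (CR) reported for the preceding study in Section 6.2. The half-width is 1.96 × √(0.86 × 0.14 / n), where n is the number seen at month 60. At d = 3%, n = 70.8 against 77.6, giving 8.1 against 7.7 points. At d = 5%, n = 65.2 against 76.0, giving 8.4 against 7.8 points. At d = 10%, n = 52.5 against 72.0, giving 9.4 against 8.0 points. The loss of precision is modest; the main cost is later events that go unobserved.

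**What return does not recover.** Sustained CR (endpoint 1) requires absence of disease at all endoscopies through month 60. Under independence, the share with all four endoscopies is (1 − d)⁴ under both rules: 88.5% at 3% and 81.5% at 5%. A returning subject's skipped examinations stay missing. The gain is in late status, later recurrence or progression, durability and death.

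**The case against.** The case against is strong on several points.

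- **No contradiction.** A reader might infer that Section 9.9 contradicts itself, since it also promises follow-up of all patients to study termination. It does not. That sentence says endpoint failure and escape treatment do not end follow-up; it does not promise data on people who cannot be found. The next sentence limits completion to patients not withdrawn or disqualified.
- **A missed visit is not loss.** A reader might infer that one missed yearly visit, or four weeks of silence, means exit. The four weeks start only after the calls, the letter and the approach to the practitioner. A subject who misses a visit but answers is not naturally read as lost.
- **Finality is inferred.** The text neither says that exit is permanent nor bars return. This stands as a matter of wording. But the form is the one used for withdrawals, its remark ties it to study completion, and no way back is described. Permanent exit is therefore a likely operational reading.
- **Section 6.2 does not blame unreachable patients.** It also lists lesions left untreated and inadequate follow-up after recurrence or progression was detected.
- **Partly handled.** Events before loss are already counted. Protocol Section 13.6 and SAP Section 7.4 plan compliance tables, withdrawals with reasons, and sensitivity analyses that may include multiple imputation and tipping point. These help, but none recovers an unobserved cancer or death. Last observation carried forward, also listed, would carry CR forward for a responder exited while in CR.

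**Conclusion.** The point holds as an inexpensive improvement to an operative rule. One failed contact procedure, at any visit, leads to the exit form, and the documents provide no renewed contact, no return and no end-of-study vital-status step. Followed as written, this can give up recoverable data on recurrence, progression, durability and ESCC mortality.

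The size cannot be derived from the documents. Under assumed independent non-contact of 3% to 5% per yearly visit, and with exit treated as permanent, 11.5% to 18.5% would lack month-60 status, against 3% to 5% if all could return. That comparator is the best case for the change, and non-contact probably clusters in the same people, so the real gain is likely to be smaller. The 12-month primary endpoint precision in Section 13.2 is not called into question.

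**What to change.** In Section 9.9, replace exit after the four-week period with the following:

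- Record the visit as missed, keep the subject active, and repeat the contact steps at each remaining scheduled visit through month 60.
- Complete the Study Exit CRF as lost to follow-up only after the month-60 attempt fails, or on withdrawal.
- At that point seek vital status, cause of death and any ESCC diagnosis from hospital records or the general practitioner, where consent allows.
- State that a subject who returns may resume visits, and that the skipped endoscopies remain missing for sustained CR.

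The cost is a paragraph in Section 9.9, matching exit-form instructions, a few more calls and letters per non-attending subject, and later closure of exit forms. No new visits are needed.

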9.10. Definitions

-CR = complete response

Absence of MGIN or worse in biopsies from TA at a single endoscopy.

- Escape treatment

Escape treatment is indicated for lesions with (i) ESCC in biopsies, (ii) non-flat lesions, or (iii) lesions otherwise suspicious for ESCC (e.g. pink-sign positive lesions). Escape treatment will be performed by investigator's distinction and per hospital's standards of care. Subsequent pathology assessment determines whether patient is defined as progressor and failure for the efficacy endpoint.

- Progressive disease

This term is applicable during the whole study. Progressive disease is defined as ESCC in any biopsy or resection specimen. Progressive disease on biopsy will always be treated with escape treatment.

Patients with progressive disease within the first 12 months are a failure for the primary efficacy endpoint, whereas progression patients in subsequent 4 years of follow-up are a failure for the durability endpoint. Progressive disease can be classified into 2 categories based on pathology:

- Eligible for endoscopic treatment, if all of the following characteristics are met: good to moderate differentiation, negative vertical resection margins, m1/m2/m3/sm1 disease and without lymphovascular infiltration.
- Exceeding the limits for endoscopic treatment, if any of the following characteristics was found: poor differentiation, positive vertical resection margins, sm-2 or sm-3 invasion or lymphovascular invasion.

- Treatment failure

This term is applicable to the first 12 months of study. All patients with residual ESCN at the 12 months endoscopy, and patients who progressed to ESCC before 12 months, will be defined as treatment failures.

- Sustained CR

This term is applicable during follow-up, to all patients that were not defined as treatment failures at 12 months. Sustained CR is defined as sustained eradication of MGIN or worse in biopsies from TA, during all FU endoscopies until 60 months.

- Recurrent disease

This term is applicable during follow-up, to all patients that were not defined as treatment failures at 12 months. Recurrent disease is defined as flat (Paris type 0-IIb) USLs with MGIN or HGIN in biopsies from TA during FU, independent of baseline pathology. Recurrent disease will be treated with RFA initially, or escape treatment if persistent, as described in section 9.4.3

10. Risks and Benefits

10.1. Potential Risks

Potential risks of the use of the Barrx™ Flex Radiofrequency Ablation System for treatment of ESCN have been evaluated in Clinical Evaluation Reports for the Barrx™ Circumferential Radiofrequency Ablation System (REG-0023, Revision C, August 12, 2014), the Barrx™ Focal Radiofrequency Ablation System (REG-0022, Revision B, December 6, 2013), and the product Instructions for Use (Ref 32041-18, 32041-22, 32041-25, 32041-28, 32041-31, 3441C; Version 717-0050-01 B and Ref 90-9100, 90-9200, 90-9300; Version 717-0053-01 B).

Medtronic Confidential

10.2. Potential Benefits

Potential benefits to the subject include the potential for complete eradication of ESCN, which has been reported in the literature with rates between 50% and 100% (11, 18, 19, 23-25, 27, 28).

10.3. Risk-Benefit Rationale

As described in the Clinical Evaluation Reports referenced above, risk analyses for the Barrx™ Circumferential Radiofrequency Ablation System and the Barrx™ Focal Radiofrequency Ablation System was conducted in compliance with ISO 14971-Risk Management for Medical Devices. The overall evaluation of the residual system risks found no unacceptable design or process hazards of significant impact to the safety and reliability of the Barrx™ Radiofrequency Ablation System. The residual risks have been rated as either broadly acceptable or as low as possible.

11. Adverse Events and Device Deficiencies

11.1. Definitions/Classifications

Adverse Events

Adverse event (AE) definitions used in this study are based on ISO 14155:2011 (Clinical Investigation of Medical Devices for Human Subjects -- Good Clinical Practice). Adverse events will be collected starting from enrollment into the study.

Adverse Event (AE)

An Adverse Event is any untoward medical occurrence, unintended disease or injury, or untoward clinical signs (including abnormal laboratory findings) in subjects, users or other persons, whether or not related to the investigational medical device.

NOTE 1 This definition includes events related to the investigational medical device or the comparator.

NOTE 2 This definition includes events related to the procedures involved.

NOTE 3 For users or other persons, this definition is restricted to events related to investigational medical devices.

Serious Adverse Event (SAE)

A Serious Adverse Event is an adverse event that has

a) Led to death,

b) Led to serious deterioration in the health of the subject, that either resulted in

1) A life-threatening illness or injury, or

Medtronic Confidential

- 2) A permanent impairment of a body structure or a body function, or
- 3) In-patient or prolonged hospitalization, or
- 4) Medical or surgical intervention to prevent life-threatening illness or injury or permanent impairment to a body structure or a body function,

c) Led to fetal distress, fetal death or a congenital abnormality or birth defect

NOTE: Planned hospitalization for a pre-existing condition, or a procedure required by the clinical investigational plan, without serious deterioration in health, is not considered a serious adverse event.

Adverse Device Effect (ADE)

An Adverse Device Effect is an adverse event related to the use of an investigational medical device.

NOTE 1 This definition includes adverse events resulting from insufficient or inadequate instructions for use, deployment, implantation, installation, or operation, or any malfunction of the investigational medical device.

NOTE 2 This definition includes any event resulting from use error or from intentional misuse of the investigational medical device.

Serious Adverse Device Effect (SADE)

A Serious Adverse Device Effect is an adverse device effect that has resulted in any of the consequences characteristic of a serious adverse event.

Unanticipated Serious Adverse Device Effect (USADE)

An Unanticipated Serious Adverse Device Effect (USADE) is defined as serious adverse device effect which by its nature, incidence, severity or outcome has not been identified in the current version of the risk analysis report.

Adverse Event Severity Classification

Severity will be defined according to the following criteria:

Mild	Awareness of event, but easily tolerated
Moderate	Discomfort enough to cause some interference with activities of daily living (ADL)

Severe

Incapacitating, with an inability to perform ADL

An AE can be classified as severe and not deemed a SAE. Similarly, a SAE is not automatically severe in nature.

Adverse Event Relationship Classification

Causality assessments define the relationship between the use of the medical device (including the medical-surgical procedure) and the occurrence of each adverse event. During causality assessment activity, clinical judgment shall be used and the relevant documents, such as the Clinical Evaluation Report and the Risk Management Report shall be consulted, as all the foreseeable serious adverse events and the potential risks are listed and assessed there. The presence of confounding factors, such as concomitant medication/treatment, the natural history of the underlying disease, other concurrent illness or risk factors shall also be considered.

Each AE and SAE will be classified according to five different levels of causality. The sponsor and the investigators will use the following definitions to assess the relationship of the serious adverse event to the investigational medical device or procedures:

- **Not related:** relationship to the device or procedures can be excluded when:
 - the event is not a known side effect of the product category the device belongs to or of similar devices and procedures
 - the event has no temporal relationship with the use of the investigational device or the procedures;
 - the serious event does not follow a known response pattern to the medical device (if the response pattern is previously known) and is biologically implausible;
 - the discontinuation of medical device application or the reduction of the level of activation/exposure - when clinically feasible – and reintroduction of its use (or increase of the level of activation/exposure), do not impact on the serious event;
 - the event involves a body-site or an organ not expected to be affected by the device or procedure;
 - the serious event can be attributed to another cause (e.g. an underlying or concurrent illness/ clinical condition, an effect of another device, drug, treatment or other risk factors);
 - the event does not depend on a false result given by the investigational device used for diagnosis, when applicable;
 - harms to the subject are not clearly due to use error;
 - In order to establish the non-relatedness, not all the criteria listed above might be met at the same time, depending on the type of device/procedures and the serious event.
- **Unlikely:** the relationship with the use of the device seems not relevant and/or the event can be reasonably explained by another cause, but additional information may be obtained.
- **Possible:** the relationship with the use of the investigational device is weak but cannot be ruled out completely. Alternative causes are also possible (e.g. an underlying or concurrent illness/ clinical condition or/and an effect of another device, drug or treatment). Cases were relatedness cannot be assessed or no information has been obtained should also be classified as possible.
- **Probable:** the relationship with the use of the investigational device seems relevant and/or the event cannot reasonably be explained by another cause, but additional information may be obtained.
- **Causal relationship:** the serious event is associated with the investigational device or with procedures beyond reasonable doubt when:
 - the event is a known side effect of the product category the device belongs to or of similar devices and procedures;
 - the event has a temporal relationship with investigational device use/application or procedures;
 - the event involves a body-site or organ that
 - the investigational device or procedures are applied to;
 - the investigational device or procedures have an effect on;
 - the serious event follows a known response pattern to the medical device (if the response pattern is previously known);
 - the discontinuation of medical device application (or reduction of the level of activation/exposure) and reintroduction of its use (or increase of the level of activation/exposure), impact on the serious event (when clinically feasible);

- other possible causes (e.g. an underlying or concurrent illness/ clinical condition or/and an effect of another device, drug or treatment) have been adequately ruled out;
- harm to the subject is due to error in use;
- the event depends on a false result given by the investigational device used for diagnosis, when applicable;
- In order to establish the relatedness, not all the criteria listed above might be met at the same time, depending on the type of device/procedures and the serious event.

The sponsor and the investigators will distinguish between the serious adverse events related to the device and those related to the procedures (any procedure specific to the clinical investigation). An adverse event can be related both to procedures and the device. Complications of procedures are considered not related if the said procedures would have been applied to the patients also in the absence of device use/application.

In some particular cases the event may be not adequately assessed because information is insufficient or contradictory and/or the data cannot be verified or supplemented. The sponsor and the Investigators will make the maximum effort to define and categorize the event and avoid these situations. Where the sponsor remains uncertain about classifying the serious event, it should not exclude the relatedness and classify the event as “possible”.

Adverse Event Outcome Classification

Outcome of the event will be defined according to the following:

- *Resolved*: The event has fully resolved at the end of the study.
- *Resolved with sequelae*: The event has resolved, but retained pathological conditions resulting from the prior disease or injury.
- *Continuing*: The event is ongoing at the end of the study.
- *Death*: This event is determined to be the cause of death.

